2.3 Variables

The main aim of this study is to describe and quantify differences in patients who alert in different NHS Trusts. The 'key exposure' is the algorithm used to define the sepsis alert in the five NHS Trusts. Variables of interest are identified in Table 2.

Table 2 Empty table to illustrate proposed data collection for Study 1. Superscript numbers refer to specific questions shown at the end of the document.

NHS Trust	Α		В		С		D		Е	
Sepsis alert algorithm	Red Flag	SoS	NEWS2	SoS	Red Flag	SoS	Oxford's alert	SoS	SJSA	SoS
Frequency										
Total Number of alerts in 12										
months										
Seasonal variation in alerts										
Shift (time) of alert ¹										
Patient characteristics ²										
%Male										
Age – median and IQR										
Ethnicity										
Comorbidities ³ /Conditions on										
discharge										
>Diabetes										
> Immuno-compromised										
Deprivation										
Location of alerts ⁴										
%ED										
%other key wards										
Process measures ⁵										
Received IV antibiotics										
Received IV antibiotics within 3		NA		NA		NA		NA		NA
hrs of alert										
Blood test ordered										

Blood test ordered within 3 hrs	NA	NA	NA	NA	NA
of alert.					
Lactate measurement					
Lactate measurement within 3	NA	NA	NA	NA	NA
hrs of alert					
Outcomes					
Length of stay for those who					
alert in the ED					
Admission to ICU after alert					
Mortality – 7 days					
Mortality – 30 days					
Impact on coding/formal					
diagnosis					
Proportion with a sepsis code at					
discharge/death					
Proportion with a SoS code at	NA	NA	NA	NA	NA
discharge/death					
Alert specific response	NA	NA	NA	NA	NA

2.4 Data sources/ measurement

All data are extracted from electronic health records and are part of routinely collected data stored within patient records. As part of the NIHR-Health Informatics Collaborative data managers at each trust shared data through a secure data-sharing platform All data was quality checked and processed by the data warehouse team at ICHT.

2.5 Bias

In order to compare the impact of different algorithms on the characteristics and patterns of alerting, the case-mix being admitted to the hospital is the key source of bias. All hospitals are in a similar region of England, but the intake of the five hospitals is different in terms of ethnicity, age and deprivation. In order to determine if the algorithm is the key factor determining differences in the profiles of the patients who alert we compared the profile with patients discharged with an ICD-10 SoS code.

2.6 Study size

Five NHS Trusts are included in this study. The number of patients included in the study is determined by the number of patients who alerted. The power to detect differences will be determined post-hoc.

2.7 Quantitative variables -

Ethnicity – ethnicity coding is based on recorded ethnicity using NHS ethnicity codes. Due to small numbers some groups will be combined into standard combinations for statistical comparisons. Age – We will categorise age into 10-year age groups. For statistical comparisons we will combine smaller groups.

Ward of alert – The primary factor for analysis is whether alerts fired in the ED or inpatient wards. This is consistently documented across the NHS Trusts. For some Trusts we were able to determine whether alerts fired in acute wards,

IV antibiotics – Within EHRs medications are categorised as antibiotics and route of administration. Blood tests – EHRs contain orders for microbiology tests, including the date and time.

Lactate - EHRs include lactate results. Lactate is a point of care test in all Trusts included in the study. Length of stay - Length of stay, measured in hours, was determined from the date and time of admission and discharge recorded in the patient record. For this descriptive study we will quantify length of stay for patients who are discharged alive.

Mortality – mortality was based on discharge destination recorded in the EHR. For the purposes of this study only in-hospital mortality was available for all NHS trusts.

2.8 Missing data

Patient admissions will not be excluded if patient data is missing, an additional category of missing will be included for age, gender, ethnicity and deprivation. As part of quality checks, we will confirm whether there are any patterns in missing data, for example periods of time where no lactate were reported. Our experience of EHRs indicate that there can be periods of missing data relating to EHR downtime.

3. Statistical methods

(a) Describe all statistical methods, including those used to control for confounding

3.1 Differences in alerting over time and between patient subgroups.

We will describe the number of first alerts in each Trust in total and over different time periods. In order to compare between Trusts we will consider the number of available overnight beds as an indication of hospital size.[2]

In addition, we will compare the alerts in the ED compared to the number of consultants in the ED. We will use a Poisson model to determine if there are significant differences in alerts during different 'shifts' days of the week and seasons. The SoS admissions in the same period will be the offset in the Poisson model.

Differences in alert frequency in patient sub-groups will be assessed within and between NHS Trusts. We will use all patients discharged with an SoS diagnosis to adjust between hospitals as a case-mix adjustment.

We will describe differences in percentages of all patients and sub-groups of patients alerting between Trusts and assess the significances in differences using chi-squared tests. As there are many patient sub-groups and therefore multiple significance tests, we will use a p-value of 0.01 to assess significance. *3.2 Association between alerting and process measures*

Process measures for inclusion are IV antibiotics, blood samples taken for microbiology and lactate measurement. We will describe process measure completion in alerting patients across Trusts, and subgroups of patients including alert location, age-groups and other sub-groups. We will consider completion of individual process measures and completion of all three within three-hours.

We will model process measure completion using a logistic regression adjusted for confounding factors, primarily patient characteristics which have been identified by clinicians as clinically associated with non-completion of process measures.

We will determine the association between the alert and completion of individual process measures, completion of the three measures, and whether the associations are different for different patient subgroups.

We will model each Trust separately and also model all patients in a multi-level model with clustering at Trust level. We will determine the sensitivity of results to the modelling approach.

Association between alerting and patient outcomes

We will assess the association between alerting and patient outcomes using a competing risks survival analysis with discharge and death as competing risks. This will allow us to fully adjust for patient factors and consider both patients who survive to discharge and those who do not. We will include process measure completion as time varying covariates.

In addition, we will separately model ICU admission after alerting using both a survival analysis and logistic model.

Association between alerting and coding

We will describe the coding of alerting patients between Trusts. The Trust which does not have a sepsis specific alert will be excluded. We determine if the differences are significant using chi-squared test. We will use descriptive approaches to compare sepsis coding between Trusts in patients with a SoS code. We will also consider whether the patterns are the same across the main patient subgroups. Statistical significance will be assessed using chi-squared tests.

(b) Methods used to examine subgroups and interactions

Within each model we will separately consider subgroups when we perform our analysis. We will consider a priori interactions.

(c) Missing data

Missing data will be included as a category on its own for factors such as ethnicity and deprivation. We will inspect data to identify periods of missing data which may be a result of EHR downtime, if necessary we will consider imputation.

We will ensure from clinicians that all process outcomes are likely to be recorded in the EHR and policy for carrying out the processes are the same across all Trusts.

Bibliography

[2] NHS Bed Availability and Occupancy Data – Overnight. Available from:

https://www.england.nhs.uk/statistics/statistical-work-areas/bed-availability-and-occupancy/bed-data-overnight/


Quantifying the impact of a digital sepsis alert on key patient outcomes and process

measures.

We will use interrupted time series with a control to determine the impact of the introduction of alerts on patient outcomes and process measures

Main cohort: patients (18+) with an SoS ICD-10 code (intervention group) at discharge OR a falls ICD-10 code (control group).

Time period: April 2010 to March 2021

General data description: patient information, admission & discharge information, A&E information and ICU admission if possible

1.Introduction

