- Increase in *Clostridium difficile* Infections (CDI): Beta-lactam use is associated with an increased risk of acquisition of CDI, with the elderly being a group particularly at risk. We will monitor *CDI* rates within each Trust over time and investigate any changes in CDI rates following introduction of digital sepsis alerts.
- Increase in short term admissions: We will examine changes in short term admissions (<24 and <48 hours) in patients diagnosed with a bacterial infectious disease.
- Increases in administration of IV antibiotics which are deemed unnecessary. We will assess through monitoring changes in numbers of patients who are administered IV antibiotics and are discharged without a Suspicion of Sepsis or other infection code.
- Increases in the use of carbapenems and/or antibiotics from the AWaRe list²⁹ these indicators are part of the sepsis CQUIN, so will be reported by each Trust

Methods of Data Analysis

Descriptive analysis

We will summarise the number of inpatient alerts and alerts in A&Es for patients aged 18 and over in each Trust, standardised by inpatient admissions and A&E attendances respectively. As alerts can fire multiple times for one patient encounter with a hospital, we will include the first alert for each patient encounter. Simple descriptive statistics will allow us to describe variations in the numbers of alerts by Trust and, where Trusts are made up of multiple sites, by site. We will describe variation in standardised alert rates with and without taking into account patient characteristics, which will include patient age, sex and pre-existing comorbidities where this information is available. Standard statistical approaches including Chi-squared tests to determine if there are differences in the characteristics of patients across Trusts and sites. Regression models will examine seasonal variations in alert frequency and whether there are trends in standardised rates over time. We will summarise patient outcomes for each Trust based on all patients who alert and patients who received a code included in the Suspicion of Sepsis list. Where Trusts utilise the same alerting approach we will compare rates of alerts, patient characteristics and patient outcomes by alert type.

Primary analysis

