1.1 Objectives (these are the objectives in the NIHR Application)

- a) Describe the total sample of patients who are affected by the alert and baseline outcome data
- b) Describe the frequency of the alert across different Trusts, departments within Trusts and specific patient groups
- c) Describe any seasonal and temporal variations in alerts across different Trusts.
- d) Describe the impact of the Covid-19 pandemic on alerting in terms of total sample, frequency, patient demographics and seasonal/temporal variations.

2. Methods

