2.1 Study design & Setting

This is a cross sectional study across five NHS Trusts in England. The period of study is 1st February 2019 to 31st January 2021, divided into two years starting 01/02/19 and 01/02/20 to consider the impact of Covid-19. The time period was selected based on the latest introduction of electronic health records across the five NHS Trusts and to separately consider patients with Covid-19 affecting the pattern of sepsis alerts.

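### The Poisson tests of shift, weekday and season differences in alerts allow for neither overdispersion nor serial correlation, and do not say how the Covid-19 year enters the model

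*Protocol*

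**What the plan says.** The first study plan in the protocol's Appendix (the comparison of alerting algorithms), section 3.1, reads: "We will use a Poisson model to determine if there are significant differences in alerts". The factors it goes on to list are shift, weekday and season. The next sentence adds: "The SoS admissions in the same period will be the offset in the Poisson model". The counts are first alerts; protocol section 7.2 says "we will include the first alert for each patient encounter".

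Section 2.1 of the same study plan sets a 24-month window from February 2019 to January 2021, which is "divided into two years starting 01/02/19 and 01/02/20 to consider the impact of Covid-19". Section 1.1 makes the pandemic an objective: "Describe the impact of the Covid-19 pandemic on alerting in terms of total sample, frequency, patient demographics and seasonal/temporal variations".

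Nothing in the statistical methods of this study plan mentions a dispersion parameter, scaled or robust standard errors, a negative binomial model or serial correlation. The two-year split is not carried into the sentence on the Poisson model. Protocol section 10 sends the reader to Appendix 1 for the detailed statistical plans, so this is where the choice is made.

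**The concern.** A Poisson model sets the variance of each count equal to its mean. If the underlying alert rate also moves from day to day for reasons outside the model, the counts vary more than that and the model-based standard errors are too small.

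The plan gives reasons to expect such movement. It anticipates periods of EHR downtime, which can remove alerts from the count. The SoS offset is built from codes assigned at discharge or death, so it need not fall at the same time. The plan also expects Covid-19 to change alerting itself: it separates the two years "to separately consider patients with Covid-19 affecting the pattern of sepsis alerts". Such a change alters the ratio of alerts to SoS admissions, which the offset treats as stable.

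At stake are the study's statements on temporal and seasonal variation in alerts. Differences between shifts, weekdays or seasons could be called significant when they are noise. A seasonal pattern in the second year could be the epidemic under another name.

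**Working it through.** The documents give no alert counts, dispersion or power for this analysis, so there is no figure of the plan's own to reproduce. The dispersion is an assumption, shown over a range. No significance level is stated for the Poisson tests. The 0.01 in section 3.1 belongs to the chi-squared subgroup comparisons, so both 5% and 1% are shown.

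**1. Error rate under overdispersion.** Let the variance be φ times the mean. The Poisson model reports a standard error that is 1/√φ of the correct one. The true two-sided error is 2 × [1 − Φ(z/√φ)], with z = 1.96 at nominal 5% and 2.576 at nominal 1%.

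| φ (assumed) | True error, nominal 5% | True error, nominal 1% | Interval width relative to correct |
|---|---|---|---|
| 1 | 5.0% | 1.0% | 100% |
| 1.2 | 7.4% | 1.9% | 91% |
| 1.5 | 11.0% | 3.6% | 82% |
| 2 | 16.6% | 6.9% | 71% |
| 3 | 25.8% | 13.7% | 58% |
| 5 | 38.1% | 24.9% | 45% |

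**2. How such values could arise.** If the daily rate varies with coefficient of variation c around a mean of m alerts per day, then φ = 1 + m·c². With c = 0.20 assumed, m = 25 gives 1 + 25 × 0.04 = 2, m = 50 gives 3 and m = 100 gives 5.

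**3. Which tests are affected by what.** Daily counts were simulated with no true weekday or season effect, at an assumed 20 alerts per day, 1,000 runs per scenario. The offset and shift were not simulated. False-positive rates at nominal 5% over 365 days:

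| Extra variation | Weekday, Poisson | Season, Poisson | Weekday, quasi-Poisson | Season, quasi-Poisson |
|---|---|---|---|---|
| None | 5.2% | 5.1% | 5.4% | 5.0% |
| Independent from day to day (log-SD 0.2, φ about 1.8) | 33.0% | 25.5% | 4.7% | 5.2% |
| Slow drift (log-SD 0.2, lag-1 correlation 0.95) | 7.0% | 95.3% | 0.0% | 92.5% |

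Over 730 days the pattern is the same. Slow drift gives 7.8% for weekday and 94.4% for season under Poisson, and season is still 90.2% under quasi-Poisson.

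Slow drift is almost balanced across weekdays, so it barely moves that test, and the same reasoning applies to shift. Under pure drift, scaling by the dispersion makes the weekday test too cautious, which is a reason to use standard errors that reflect the serial correlation rather than a scale factor alone.

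**4. Whether a variance correction rescues season.** Within one year each season is a single block of time, so it coincides with whatever else happened then. A negative binomial model with week-clustered errors, in one simulated year with no season effect and 20 alerts per day, still gave about 63%, 75% and 92% false positives. The drift settings (log-SD/lag-1 correlation) were 0.1/0.95, 0.2/0.95 and 0.3/0.98. This is confounding of season with calendar period, which better standard errors do not remove.

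**The case against.** The strongest reply is that the plan names a model family and an offset and leaves the variance estimator open. Scaled or robust errors are ordinary analysis-plan detail, and a separate analysis plan may exist. This has some force: nothing in the text forbids a dispersion check. But the protocol itself says its detailed statistical plans are in this appendix. Followed as written, the named model produces the standard errors criticised here.

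Several further points stand and limit the claim:

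- Counting only first alerts removes the clustering that repeat alerts would add.
- SoS admissions plausibly move with patient volume and infection load, so the offset will absorb some of the variation. How much cannot be known from the documents.
- The plan intends to look for downtime periods and to consider imputation.
- The study describes itself as mainly descriptive, and the mortality analysis does not depend on this model.

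A reader might infer that the plan ignores Covid-19. It does not: it splits the window at 1 February 2020 and makes the pandemic's effect an objective. What is missing is any statement that the Poisson model uses the split. The split alone would also leave the pandemic's variation inside year two.

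A reader might also infer that Covid-19 produces false shift and weekday differences. The simulation gives little support for that: slow drift left the weekday test at about 6–8%. Nor does the plan offer fluctuating bed occupancy as a source of variation; it uses available beds only as a measure of hospital size.

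**Conclusion.** The point holds in conditional form. The stated model has no protection against overdispersion or serial correlation, and its use of the two study years is undefined. If φ is 2, 3 or 5, a nominal 5% test has a true error of about 17%, 26% or 38%, and a nominal 1% test about 7%, 14% or 25%. These rates rest on an assumed φ. At φ = 1 the Poisson test is correct, so the documents do not support saying that the errors certainly will be too small. Overdispersion is nevertheless likely, because the offset need not track downtime or a Covid-19 change in alerting.

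The mechanisms differ by factor. Weekday, and by the same reasoning shift, is exposed to short-term overdispersion, which dispersion scaling repairs when that variation is independent from day to day. Season is exposed mainly to slow drift, and in year two it is confounded with the epidemic period. It would be wrong to conclude that changing the variance model settles season as well.

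**What to change.** In section 3.1 of the first study plan in the Appendix, replace the Poisson model with a quasi-Poisson or negative binomial model with serial-correlation-robust standard errors, keeping the SoS offset. State that it is fitted separately in the two study years, or with a year/Covid-19 term. Report the dispersion and give rate ratios with intervals. State the significance level for these tests, since the present 0.01 is tied to the chi-squared comparisons. Say that season contrasts in the Covid-19 year are descriptive, because no variance correction removes that confounding.

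This takes a few sentences and no new data. The price is somewhat wider intervals and giving up any significance claim for season in year two.

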2.2 Participants

All adult (18+) inpatients admitted between 01/02/19 and 31/01/21 are initially eligible for inclusion in the study. We will liaise with data managers at each NHS Trust and identify all patients who triggered a sepsis alert in each Trust. The sample of patients included in the study are adult inpatients who triggered a sepsis alert at any point in their inpatient stay or time in A&E in the 24 months of the study.

The NHS Trusts included in the study are of differing sizes and may differ in case mix. In order to compare hospitals we will use patients with a serios infection, and therefore at risk of sepsis to adjust outcomes for patients with an alert. In order to identify patients with a serious infection will use the ICD-10 codes suggested by Inada-Kim et al and classed as 'Suspicion-of-Sepsis' (SoS). Patients are identified if a patient has an SoS ICD-10 code at discharge or at death.

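### In the first appendix study, SoS admissions in the same period are not the population at risk of a first alert by shift or weekday, so the Poisson rate ratios can show spurious differences

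*Protocol*

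**What the plan says.** All of this is in the Protocol. The first appendix study compares alerting across five Trusts.

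- **Model** (Appendix, first study, section 3.1): "We will use a Poisson model to determine if there are significant differences in alerts during different 'shifts' days of the week and seasons".
- **Offset** (next sentence): "The SoS admissions in the same period will be the offset in the Poisson model".
- **Sample** (section 2.2): "adult inpatients who triggered a sepsis alert at any point in their inpatient stay or time in A&E". Section 2.7 makes ED versus inpatient ward the main location factor, so both kinds of alert are counted.
- **Events** (section 3.1): "We will describe the number of first alerts in each Trust in total and over different time periods". Section 7.2 has the same rule: "we will include the first alert for each patient encounter".
- **Other denominators**: section 7.2 has alert numbers "standardised by inpatient admissions and A&E attendances respectively". For the comparison between Trusts, section 3.1 says "we will consider the number of available overnight beds as an indication of hospital size".

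Section 10 refers the reader to this appendix for the detailed WS2 statistical plans, so the offset is a stated choice and not a detail left open.

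**The concern.** A Poisson offset should measure the exposure that can produce the count. Here it does not, for two reasons.

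1. **Timing.** A patient admitted on Friday afternoon who first alerts on a ward on Saturday night is counted in Saturday night's numerator but in Friday's denominator.
2. **Population.** Alerts are counted in all in-scope adults, while the offset counts only patients later given an SoS code. The appendix expects alerts outside that group: its Table 2 reports the proportion of alerting patients with an SoS code.

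The fitted shift and weekday ratios then depend on when SoS patients are admitted as well as on how readily patients alert. More data does not remove this bias. It only makes a false difference easier to declare significant. At stake is the description of temporal variation (objective 2.3, and objective (c) of the first appendix study), including any inference about alert load by staff shift.

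**Working it through.** The protocol gives no figure for this model, so there is nothing to reproduce. The check asks what the planned ratio would be if alerting truly did not vary by time of day or week.

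**Inputs**
- h: the period's share of clock time, with a constant number of patients present. An 8-hour night gives h = 1/3 and a weekend gives h = 2/7. The 8-hour night is an assumption.
- s: the period's share of SoS admissions (assumed; the protocol gives none).
- f: the share of first alerts timed with admission (assumed; the protocol gives none). The remaining 1 − f are spread evenly over patient-time.

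**Formula**

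Alerts in the period are proportional to f·s + (1 − f)·h. Dividing by admissions inside and outside the period gives the expected ratio when the true ratio is 1.0:

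RR = {[f·s + (1 − f)·h] / s} ÷ {[f·(1 − s) + (1 − f)·(1 − h)] / (1 − s)}

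**Example** with h = 1/3 and s = 0.20
- f = 0: (0.333/0.20) ÷ (0.667/0.80) = 1.667 ÷ 0.833 = 2.00.
- f = 0.75: (0.2333/0.20) ÷ (0.7667/0.80) = 1.167 ÷ 0.958 = 1.22.

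**Night versus day, 8-hour night**

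| f | s = 0.15 | s = 0.20 | s = 0.25 |
|---|---|---|---|
| 0 | 2.83 | 2.00 | 1.50 |
| 0.50 | 1.81 | 1.45 | 1.24 |
| 0.75 | 1.38 | 1.22 | 1.11 |
| 0.90 | 1.15 | 1.08 | 1.04 |
| 1 | 1.00 | 1.00 | 1.00 |

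**Weekend versus weekday** (h = 2/7), with 22% and 26% of SoS admissions at weekends: 1.42 and 1.14 at f = 0; 1.10 and 1.03 at f = 0.75; 1.00 at f = 1.

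**Direction.** Take a 12-hour night (h = 0.5). With s = 0.50 the ratio is 1.00 for every f. With s = 0.55 it is 0.82 at f = 0, 0.90 at f = 0.5 and 0.98 at f = 0.9, a false night deficit.

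**Season.** Suppose winter admissions are 30% higher and alerts lag admission by L days, so that a share x = L/90 crosses the season boundary. Then RR = [(1.3(1 − x) + x)/1.3] ÷ [(1 − x) + 1.3x]. This gives 0.99 for L = 2 and 0.94 for L = 10.

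**Chance of a false finding** at p < 0.01, by a Wald test on log RR, for a 12-hour night with s = 0.40. With p₁ = f·s + (1 − f)·h, SE = √(1/(N·p₁) + 1/(N·(1 − p₁))).
- f = 0.5, N = 1,000 alerts: RR = 1.23, log RR = 0.205, SE = 0.0636, z = 3.22. Power is Φ(3.22 − 2.58), about 74%.
- f = 0.75: RR = 1.11. The chance is about 17% with 1,000 alerts and 85% with 5,000.
- f = 0.9: RR = 1.04. The chance is about 3% with 1,000 alerts and 13% with 5,000.

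The 0.01 level is borrowed from the subgroup chi-squared tests in section 3.1; no level is stated for the Poisson model. The numbers of alerts are assumptions.

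**With the offset matched to the population at risk**, the same no-effect scenario has an expected ratio of 1.00 for every contrast.

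**The case against.** Most of the case on the other side concerns how far the point reaches, and much of it stands.

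- A reader might infer that the model must produce false night and weekend excesses. The protocol does not support this. It gives no SoS admissions by hour or weekday; level admissions give no bias, and heavier night admissions reverse it.
- A reader might take the ratios of 2.8 or 1.42 as the expected error. They are the extreme case in which no first alert is tied to admission. Only first alerts are counted, and ED alerts follow arrivals, so the true size could be much smaller, down to nil.
- A reader might extend the criticism to season. A stay is short against a season and the effect is small.
- A reader might see a contradiction with the admissions, attendance and bed denominators. Those serve comparisons between Trusts, and SoS patients are a deliberate case-mix reference throughout this appendix. Inpatient admissions counted by shift would have the same timing mismatch.
- Objective 2.2 (frequency by Trust, department and patient group) is not what this model addresses.
- The period is not defined, and the model follows a sentence about ED alerts. If it were meant for ED alerts alone, the timing mismatch would shrink. The text does not say so, and SoS admissions would still not be ED attendances.
- Raw alert counts by period and by shift are also reported, so crude alert load stays visible. The mortality analyses are untouched.

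None of this makes SoS admissions in a shift the population at risk during that shift.

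**Conclusion.** The stated offset is wrong for the shift and day-of-week contrasts and should be changed. Applied as written, it yields ratios that combine alert propensity with the admission pattern, and they can differ from 1 when alerting does not vary at all. Direction and size cannot be fixed from the protocol. Under the assumed night shares the false ratio lies anywhere from 2.8 down to 1.0, depending mainly on how many first alerts coincide with admission, and other admission patterns turn it into a deficit. These figures rest on a constant number of patients present and a constant alert hazard for alerts not tied to admission. The population mismatch was not sized separately; it adds distortion only where the relation between SoS admissions and all patients at risk changes from period to period. This is a secondary, descriptive model, so the matter is moderate, but the error is systematic and cheap to avoid.

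**What to change.** In section 3.1 of the first appendix study, for shift and day of week:

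1. **Ward alerts:** use as offset the log of patient-hours at risk in the period, meaning patients present, within the alert's scope and not yet alerted.
2. **ED alerts:** fit a separate model with the log of A&E attendances in the period as offset.
3. **If data on all in-scope patients are not extracted:** use aggregate occupancy counts for the wards, or restrict both the alerts and the patient-hours to SoS-coded patients, whose admission, discharge and alert times are in the cohort.
4. Define what counts as a period, and keep SoS admissions as the case-mix comparator between Trusts.

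**Cost.** The change takes a few sentences and one derived person-time variable. Admission and discharge times are already used for length of stay (section 2.7). The cohort in section 8 and in the appendix consists of alerting and SoS-coded patients, so the full version needs records beyond it or an aggregate occupancy request. Section 3 of the protocol records that extraction stopped and that an amendment is being submitted, so such a request may take time. The SoS-only version needs no new records, but its results apply only to SoS patients.
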